2.4. Study Design

Overview of Study Design and Key Features	
	
sessions (Figure 1). The first two subjects in Part A will have up to three ⁸⁹Zr PET scans, while the remaining subject will undergo up to two ⁸⁹Zr PET scans.
 
 ○ Part B will complete up to three subjects who participate in only one anti-SAP dosing session (Figure 2). Subjects will undergo up to two ⁸⁹Zr PET scans. 
Part B will be triggered by the sponsor in consultation with the Principal Investigator. This will be based on data obtained in Part A, which includes but is not restricted to equivocal myocardial uptake of ⁸⁹Zr-GSK2398852 in all subjects treated in Part A. This decision will also be contingent based on emerging data from the concurrent Phase 2 trial (Study Number 201464). Should Part B not be triggered, then the study will conclude with Part A.

Dosing	
 • Details of the administration of CPHPC is provided in the protocol Section 5.4 • Details of the administration and dosing of Anti-SAP Treatment and ⁸⁹Zr-GSK2398852 is provided in the protocol Section 5.6 & Section 5.13
Time & Events	
 • Details of the Schedule of Activities can be found in Appendix 2, Section 12.2
Treatment Assignment	This is an open-label, non-randomised, adaptive, dose-ranging study.
Interim Analysis	
There are two types of interim analysis planned in this study:
 
 • In-stream data reviews: Data will be reviewed on an ongoing basis throughout the study (including, but not limited to: safety, imaging (PET), PK data) to make decisions on: (i) intra (i.e. subsequent dose administered within a given subject) and inter (i.e. dose administered in a separate subject) mass dose levels; and (ii) the timing of PET scan. • Interim analysis at the end of Part A: once the last subject in Part A has completed their final dosing session, a formal review of all available safety data (including AEs, clinical laboratory data, vital signs, ECGs), PK, PET imaging data will be conducted before deciding whether to trigger Part B.

2.5. Statistical Analyses

This is an exploratory study where the primary objective is to assess cardiac uptake of ⁸⁹Zr-GSK2398852 evaluated by PET imaging at different mass doses. No formal hypotheses will be tested as part of this study.

All generated PET imaging endpoints (e.g., SUV_{peak}, SUV_{mean}, SUV_{total_organ} etc.) over time will be listed to identify the potential for cardiac uptake of ⁸⁹Zr-GSK2398852 in ATTR-CM patients.

2.6. Sample Size Considerations

At the time of writing no empirical data was available to offer a suitable estimate for the expected between subject variability; therefore, the sample size has been determined primarily by feasibility.

A total of 6 subjects are expected to complete up to two dosing sessions. The study is split into two parts:

- in Part A up to 3 subjects will participate in up to two anti-SAP dosing sessions
- in Part B up to 3 subjects will participate in one anti-SAP dosing session.

Data will be reviewed in-stream with a view to inform subsequent unlabelled anti-SAP mAb mass dose levels.

No sample size re-estimation is planned for this study; however, at the interim (i.e. at completion of Part A) the team may decide to stop the study early and not recruit any subjects into Part B.

3. PLANNED ANALYSES

3.1. Interim Analyses

Decision making for the development programme is time critical and therefore there are two types of interim analysis planned in this study:

- **In-stream data review(s):** Data will be reviewed on an ongoing basis throughout the study (including, but not limited to: safety, imaging (PET), PK data). Any emergent PET imaging data from the current study will be complementary to the ongoing phase II study (Study Number 201464) and its associated interim(s), as well as the broader Anti-SAP program. In addition, during the current study, team review of listings of accruing uncleaned study data (provided directly by Data Management or obtained from site) may trigger changes being made to a number of design parameters, including: (i) subsequent dose levels for the same or future subjects; and (ii) the timing of PET scan, all based on the emerging data. The foreseen primary parameters for this in-stream review is anticipated to be cardiac SUV values plus plasma radio-PK in relation to administered mass dose.
- **Interim analysis at the end of Part A:** once the last subject in Part A has completed their final dosing session, a formal review of all available safety data (including AEs, clinical laboratory data, vital signs, ECGs), PK, PET imaging data will be conducted before deciding whether to trigger Part B. Study data included as part of this interim will be cleaned prior to analysis.

Details for end of Part A interim include

- Plots of individual profiles, listings and tabulated descriptive statistics where appropriate for: blood pressure, heart rate, AEs, clinical chemistry, hematology, urinalysis, cardiac monitoring, NT-ProBNP, Troponin T, serum Creatinine, eGFR
- Listings of PET imaging parameters
- Plots of plasma concentration of GSK2398852, for radioactive assays, versus time.

3.2. Final Analyses

The final planned primary analyses (which will comprise both Part A and the optional Part B together) will be performed after the completion of the following sequential steps:

1. All participants have completed the study as defined in the protocol (which may or may not include participants from Part B following the decision as to whether to trigger Part B based on the interim analysis at the end of Part A).
2. All required database cleaning activities have been completed and final database release (DBR) and database freeze (DBF) has been declared by Data Management.
3. The study has a non-randomised open label design, however, for internal study reporting, subjects will be assigned randomisation numbers. Therefore, the formal process for unblinding the randomization codes will need to be also met.
4. Randomization codes have been distributed according to RandAll NG procedures.

4. ANALYSIS POPULATIONS

Population	Definition / Criteria	Analyses Evaluated
Screened	Comprises of subjects who sign the Informed Consent	Screen failures
Enrolled	Comprises of subjects who ultimately pass screening, even if rescreened. The following subjects are included in the Enrolled population: Subjects who have been assigned a randomisation code. Screen failures are excluded from the enrolled population.	Study Population (Selected Outputs)
All Treated	All subjects who receive at least one Anti-SAP treatment including ⁸⁹ Zr-GSK2398852	PET
Safety ¹	All subjects who receive at least one dose of GSK2315698, GSK2398852, or ⁸⁹ Zr-GSK2398852. As all patients who receive GSK2398852, or ⁸⁹ Zr-GSK2398852 will also have received GSK2315698 (as mandated by the protocol), this definition is equivalent to all subjects who received at least one dose of GSK2315698	Study Population Safety PD/Biomarkers
Pharmacokinetic (PK)	All subjects from the All Treated Population for whom a PK sample is obtained and analysed	PK

Refer to [Appendix 9](#): List of Data Displays which details the population used for each display.

Notes

[1] Population identified separate from “All Treated” as described in protocol. Here exposure to any administered GSK compound warrants belonging to the “Safety” population

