## **8. DISCONTINUATION CRITERIA**

### **8.1. Discontinuation of Study Treatment**

#### **8.1.1. Discontinuation for failure to deplete plasma SAP levels with IV CPHPC**

Subjects will be withdrawn from the study if they are unable to deplete plasma SAP levels to target (Section 5.4 and Section 5.5).

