### 10.3.1. Populations for Analyses

For purposes of analysis, the following populations are defined:

- **All Treated Population:** defined as all subjects who receive at least one Anti-SAP treatment including  $^{89}\text{Zr}$ -GSK2398852. All safety analyses will be evaluated on this analysis population.
- **The PK Population:** defined as all subjects from the All Treated Population for whom a PK sample is obtained and analysed.

Additional analysis populations may be defined in the Reporting and Analysis Plan (RAP).

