2.1. Nomenclature

In this document:

- GSK2315698 is referred to as CPHPC (carboxy pyrrolidine hexanoyl pyrrolidine carboxylate).
- GSK2398852 is referred to as unlabelled anti SAP mAb.
- ⁸⁹Zirconium-desferrioxamine (Df) labelled anti-SAP mAb is referred to as ⁸⁹Zr-GSK2398852.
- The administration of CPHPC and anti-SAP mAb is referred to as Anti SAP treatment.
- Total Mass Dose (TMD) of anti-SAP mAb = unlabelled anti-SAP mAb + ⁸⁹Zr-GSK2398852.
- Throughout this document, the usage of Total mAb (or Total anti-SAP mAb) refers to both unlabelled and labelled mAb.

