8.1. Adverse Events Analyses

Adverse events analyses including the analysis of adverse events (AEs), Serious (SAEs) and other significant AEs will be based on GSK Core Data Standards. The details of the planned displays are provided in [Appendix 9: List of Data Displays](#). Tables will present AEs in the treatment phase. Listings will present all AEs

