12.3. Appendix 3: Study Phases and Treatment Emergent Adverse Events

12.3.1. Treatment Phases

Treatment phases are defined for the purpose of AE summaries and listings.

AEs will be assigned to pre-treatment, on-treatment, and post-treatment phases according to the date/time of occurrence relative to Dates/Times of First and Last Doses of Study Drug.

Treatment Phase	Definition
Pre-Treatment	Date/Time of AE < First Dose Date/Time of Study Drug ¹
On-Treatment	First Dose Date/Time of Study Drug ¹ ≤ Date/Time of AE ≤ Last Dose Date/Time of Study Drug ² + 56 Days
Post-Treatment	Date/Time of AE > Last Dose Date/Time of Study Drug ² + 56 Days

¹Earliest dose of GSK2315698 or GSK2398852 or 89Zr-GSK2398852 in the study

²Latest dose of GSK2315698 or GSK2398852 or 89Zr-GSK2398852 in the study

Unless stated otherwise, AE summaries will only include AEs assigned to the on-treatment phase. All AE listings will include treatment phase assignment.

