12.3.3. AE Onset Time and Duration

The following AE onset times and duration will be included in all AE listings.

	Definition
AE Onset Day Since First Dose of Study Drug ¹ (Days)	If First Dose Date/Time of study drug ¹ > AE Onset Date/Time, Onset Day = AE Onset Date - First Dose Date If First Dose Date/Time of study drug ¹ ≤ AE Onset Date/Time, Onset Day = AE Onset Date - First Dose Date + 1 Day Missing if subject is not exposed to any study drug
AE Onset Day Since Treatment Session First Dose of CPHPC (Days)	If Session CPHPC First Dose Date/Time of study drug > AE Onset Date/Time, Onset Day = AE Onset Date – Session CPHPC First Dose Date If Session CPHPC First Dose Date/Time of study drug ≤ AE Onset Date/Time, Onset Day = AE Onset Date – Session CPHPC First Dose Date + 1 Day Missing if AE not assigned to treatment session
AE Onset Day Since Treatment Session First Dose of mAb (Days)	If Session mAb First Dose Date/Time of study drug > AE Onset Date/Time, Onset Day = AE Onset Date – Session mAb (labelled or unlabelled) First Dose Date If Session mAb First Dose Date/Time of study drug ≤ AE Onset Date/Time, Onset Day = AE Onset Date – Session mAb (labelled or unlabelled) First Dose Date + 1 Day Missing if AE not assigned to treatment session
Duration (Days)	AE Resolution Date – AE Onset Date + 1
Drug-related	If relationship is marked 'YES' on Inform/CRF OR value is missing.

¹Earliest dose of GSK2315698 or GSK2398852 or 89Zr-GSK2398852 in the study

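### No AE table isolates the period after the mAb: SAP Tables 3.1-3.8 pool the CPHPC-only lead-in, and anyone given CPHPC alone, with post-mAb events

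*SAP*

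**What the plan says.** Protocol 10.3.1 defines the All Treated Population as subjects with at least one Anti-SAP treatment including the tracer, and adds: "All safety analyses will be evaluated on this analysis population".

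SAP Section 4 keeps All Treated for PET but moves safety to a new Safety population. One dose of any study drug is enough. Since CPHPC always comes first, "this definition is equivalent to all subjects who received at least one dose of GSK2315698". A note to the table declares the departure: "Here exposure to any administered GSK compound warrants belonging to the" Safety population. SAP 2.2, the section for changes to the protocol-defined analysis, does not list it.

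On timing, SAP 8.1 says "Tables will present AEs in the treatment phase", and SAP 12.3.1 says "Unless stated otherwise, AE summaries will only include AEs assigned to the on-treatment phase". That phase starts at the earliest dose of CPHPC, unlabelled mAb or labelled mAb, and ends 56 days after the last dose of any of them. Under SAP 12.9.2 the columns are Part A, Part B and both together, or a single *Anti-SAP* column if Part B does not run. Treatment sessions are defined for AE listings only (SAP 12.3.2).

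Both documents define the regimen alike; in the SAP's words, "The administration of CPHPC and anti-SAP mAb is referred to as Anti SAP treatment".

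**The concern.** The safety endpoint names rash, cardiac events and infusion-related reactions. Protocol 3.4.1 discusses all three as risks, identified or potential, of the mAb. In the SAP, rash is flagged in a listing and infusion reactions are listed (8.2), so Tables 3.1-3.8 hold the only tabulated AE incidence. None of them starts at the mAb.

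Protocol 9.3.4.1 records background arrhythmia before treatment so that arrhythmias are not wrongly attributed to the mAb. An undivided phase works against that aim in the tables. The drug-related tables do not help, because SAP 12.3.3 uses one yes-or-missing flag for relatedness and does not separate CPHPC from mAb.

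The tables are also interim deliverables (SAP 12.9.7), available for the formal safety review that precedes the decision on Part B (SAP 3.1).

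**Working it through.** The documents give no event rate or power for this point. The only sample size is the feasibility figure, 3 + 3 = 6, so the check is direct arithmetic.

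**Inputs.** N = 3 mAb-treated subjects in Part A, or 6 in both parts. Lead-in is about 48 h of IV CPHPC before the mAb (Protocol 5.4), up to 72 h (Protocol 7.1). Last CPHPC dose is on Day 11 (Protocol 5.12.1.1). Categorical summaries are counts and percentages of subjects (SAP 12.4.3). The number k of subjects given CPHPC but never mAb is not in the documents; I assume 0 to 2.

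**1. Mixing (needs no CPHPC-only subject).** Let *a* be subjects with the event after the mAb and *b* subjects with it only in the lead-in. The table shows (a + b)/N; post-mAb incidence is a/N. For N = 3:

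| a | b | Table | Post-mAb |
|---|---|---|---|
| 0 | 1 | 1/3 = 33.3% | 0/3 = 0% |
| 1 | 1 | 2/3 = 66.7% | 1/3 = 33.3% |
| 2 | 1 | 3/3 = 100% | 2/3 = 66.7% |

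**2. Dilution (needs k ≥ 1).** With x mAb-treated subjects affected and no event in the CPHPC-only subjects, the table shows x/(N + k):

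| N | x | k = 0 | k = 1 | k = 2 |
|---|---|---|---|---|
| 3 | 1 | 33.3% | 1/4 = 25.0% | 1/5 = 20.0% |
| 3 | 3 | 100% | 3/4 = 75.0% | 3/5 = 60.0% |
| 6 | 1 | 16.7% | 1/7 = 14.3% | 1/8 = 12.5% |

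The tables of AEs in at least 5% of subjects keep the same rows, because one subject reaches 5% for any N up to 20 (1/20 = 5%).

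**3. Direction.** The two effects oppose each other. With N = 3, k = 1, one post-mAb event and one event in the CPHPC-only subject, the table shows 2/4 = 50.0% against 1/3 = 33.3% post-mAb.

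**4. Length of the lead-in (one session).** Two days are 2/25 = 8.0% of the time to the Day 26 visit. The on-treatment window runs to Day 11 + 56 = Day 67, so the share there is 2/66 = 3.0%. With a one-day delay these become 3/26 = 11.5% and 3/67 = 4.5%.

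**5. Untimed events on the mAb date.** SAP 12.6.2 sets a missing start time to 00:00 unless the date is that of a session's first study drug dose, which is Day 1 CPHPC. An untimed AE on Day 3 is therefore placed before the infusion, and the SAP 12.3.3 formula gives onset day 3 − 3 = 0. SAP 8.2 does the opposite for potential infusion events: an untimed AE with one of its listed terms, dated on the infusion day or the day after, is included.

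**The case against.** The strongest reply is that the Safety population is right as it stands. CPHPC is investigational, has its own entry in the risk table (epistaxis, Protocol 3.4.3), and is part of Anti-SAP treatment, which is what the safety objective concerns. An any-dose set omits no exposed subject. Protocol 10.3.1 lets the analysis plan define further populations, and SAP Section 4 declares this one. That stands; the gap in SAP 2.2 is one of record.

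It is also fair that the listings hold what is needed. Every AE listing gives onset day since the session's first mAb dose (SAP 12.3.3), potential infusion events are listed around the infusion (SAP 8.2), and rash and grade have listing columns (SAP 12.9.11). With three to six subjects a reader can sort events by hand, apart from untimed Day 3 events.

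A reader might infer three stronger things that the documents do not support:

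- *That the lead-in days dilute event rates.* The tables have no person-time denominator. Extra days can only add events and raise a percentage.
- *That dilution by subjects is built in.* It needs someone given CPHPC and never mAb. Failed depletion ("Subjects will be withdrawn from the study if they are unable to deplete plasma SAP levels to target"), the renal criteria (Protocol 8.1.3) and a delay over one day without return (Protocol 5.4) allow this, and replacement is permitted (Protocol 5.7). But all first-in-human subjects reached the SAP target (Protocol 5.12.1.1), and with no such subject the denominators are identical.
- *That 20-27% of monitored arrhythmias would predate the mAb.* That takes inpatient days alone (2/10, or 3/11 after a delay) and a constant rate. Adding the outpatient monitoring week gives 2/17 = 12%, or 3/18 = 17%. Not every telemetry finding is an AE, and the designed comparator is the pre-treatment recording.

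**Conclusion.** The point holds as a limit on attribution in the AE tables. Tables 3.1-3.8 count from first CPHPC in anyone given CPHPC, so tabulated post-mAb incidence is unavailable. At N = 3, one subject with only a lead-in event moves the figure by a third of the column, for example from 1/3 to 2/3. Dilution is a separate, conditional effect: nil if k = 0, and 1/3 to 1/4 or 1/6 to 1/7 if k = 1. These are illustrations that rest on assumed event counts and an assumed k of 0 to 2.

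The *Anti-SAP* header makes this most visible, but it applies only if Part B does not run; otherwise the same pooling sits inside the part columns. The study is exploratory, and the primary PET result is not biased.

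**What to change.** Keep Tables 3.1-3.8 on the Safety population and add supplementary columns in SAP 8 and 12.9.7:

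- **From mAb start:** onset at or after the start of a session's first unlabelled or labelled mAb infusion and before any Session 2 CPHPC. The denominator is subjects who started any mAb infusion. This is better than All Treated, which requires the tracer and would omit a subject who began unlabelled mAb and never received it.
- **CPHPC only, before any mAb:** the Session 1 lead-in, plus subjects never given mAb.
- **Session 2 lead-in:** shown separately as following earlier mAb exposure. That dose was at least 4 weeks before (Protocol 5.9), so a late mAb event could fall here and should not be labelled CPHPC only.

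State that an AE with a missing start time on the mAb infusion date counts as post-mAb for these columns, in line with SAP 8.2 and in place of the 00:00 rule in 12.6.2. Record the change of safety population in SAP 2.2.

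The cost is SAP wording and programming on data already collected. The downside is wider tables with small counts.

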**Table 6 Proposed Duration and Timing of anti-SAP mAb and Zr-GSK2398852 administration**

Total Mass Doses of anti-SAP mAb	Proposed Duration of Unlabelled anti-SAP mAb Infusions	Planned Timing of  Zr-GSK2398852 Administration in Relation to Unlabelled anti-SAP mAb Infusion 
80 – 200 mg	1 Hour	Simultaneous administration: Both infusions administered over 1 hour & finishing at approximately the same time 
200 mg < Total Mass Dose ≤500 mg	6 Hours	Co-administration:  Zr-GSK2398852 administered over 1 hour, commencing any time after start of unlabelled anti-SAP mAb, including after its completion

If a subject experiences infusion reaction, dosing may be paused and resumed at investigator discretion.

Unlabelled anti-SAP mAb and Zr-GSK2398852 will be administered via two separate peripheral venous lines

After the first subject, there is an option (based on emerging data) that administration of Zr-GSK2398852 may be initiated at any time during the infusion or after the unlabelled anti-SAP mAb infusion has completed.

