9.1.2. Population of Interest

The pharmacokinetic analyses will be based on the “Pharmacokinetic (PK)” population, unless otherwise specified.

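### The PK population requires at least one tracer dose, so a subject who receives unlabelled anti-SAP mAb but never the tracer drops out of every total-mAb PK display, although that assay does not need the tracer (minor).

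*SAP*

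**What the plan says.** SAP section 4 builds the PK population on All Treated: "All subjects from the All Treated Population for whom a PK sample is obtained and analysed". Protocol 10.3.1 agrees: "defined as all subjects from the All Treated Population for whom a PK sample is obtained and analysed". All Treated is in turn "All subjects who receive at least one Anti-SAP treatment including" 89Zr-GSK2398852. SAP 2.1 defines the treatment itself without the tracer: "The administration of CPHPC and anti-SAP mAb is referred to as Anti SAP treatment". The tracer is therefore an extra condition on top of CPHPC and mAb.

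SAP 9.1.2 ties the analysis to this set: "The pharmacokinetic analyses will be based on the" PK population unless otherwise specified. Appendix 9 specifies nothing else. The total-mAb displays (Tables 4.2 and 4.4, Figures 4.2, 4.4 and 4.6, Listings 40 and 42) all name the PK population.

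For the Safety population the SAP does depart from All Treated, and note 1 explains that "exposure to any administered GSK compound warrants belonging to the" Safety population. SAP 2.2 mentions no matching change for PK.

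Protocol 5.6 and Table 6 give the tracer as a separate infusion. Above 200 mg TMD it is administered over 1 hour, "commencing any time after start of unlabelled anti-SAP mAb, including after its completion". Table 6 note 3 allows a similarly late start at or below 200 mg after the first subject.

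**The concern.** Total-mAb PK and radio-PK are two separate secondary endpoints. Protocol 9.4.1 says the total-mAb concentration is the sum of labelled and unlabelled antibody, so it can be measured and interpreted in a subject who received only the unlabelled part. A tracer condition makes sense for radio-PK but has no evident purpose for total-mAb PK.

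A subject who meets the exclusion would have valid concentrations that appear in no PK display, including the concentration listing. Protocol 10.3.5 points the other way: data up to completion or withdrawal are to be analysed however long treatment lasted. SAP 12.6.1 likewise intends to list all available data from withdrawn subjects, unless otherwise specified. With at most six subjects, doses that vary between them, and PK summarised by TMD, one missing subject could leave a dose level empty. PK also feeds the end-of-Part-A review described in SAP 3.1.

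**Working it through.** **Plan's own figure.** Protocol 10.2 sets the sample size by feasibility: 3 (Part A) + 3 (Part B) = 6, which agrees with the stated total. No power or precision formula applies, so the check is set logic followed by simple proportions.

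**Who is excluded**

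1. PK population ⊂ All Treated (SAP 4; Protocol 10.3.1).
2. All Treated requires the tracer at least once, counted per subject and not per session (SAP 4).
3. Hence no tracer in any session → not All Treated → not in the PK population.
4. A Part A subject with tracer in either session stays in for both. The exclusion reaches a Part B subject (one session) who misses the tracer, or a Part A subject who misses it in every session attended.

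**Can it happen?** The tracer is a separate infusion that may start during or after the unlabelled one, so mAb without tracer is possible. No passage says how often to expect it.

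**What would be lost per subject**

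- Share of planned TMD already given if the unlabelled infusion is completed = (TMD − 10)/TMD, the tracer mass being 10 mg (synopsis, Treatment Groups and Duration): 70/80 = 87.5%; 190/200 = 95.0%; 490/500 = 98.0%. An infusion cut short would give less.
- Scheduled total-mAb samples: 8 per session (Protocol Table 4), one of them taken before the infusion.
- Share of subjects: 1/3 = 33.3% of a part; 1/6 = 16.7% of the full study.

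**Illustration only.** The rate q of mAb without tracer is an assumption. Chance of losing at least one subject:

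| Assumed q | q per subject, N = 6: 1 − (1 − q)^6 | q per session, independent: 1 − (1 − q²)³(1 − q)³ |
|---|---|---|
| 2% | 11% | 6% |
| 5% | 26% | 15% |
| 10% | 47% | 29% |
| 20% | 74% | 55% |

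The last column supposes that all three Part A subjects attend two sessions and are excluded only if the tracer is missed in both. If Part B is not triggered, the same per-session assumption gives 1 − (1 − q²)³ = 0.1%, 0.7%, 3.0% and 11.5%. The result depends almost wholly on q, which the documents do not supply.

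**The case against.** The strongest reply is that this is a rare contingency in a descriptive secondary endpoint. No hypothesis is tested. The subject stays in the Safety population and would appear in Listing 6 as excluded from a population. The samples are still taken and assayed. In-stream dose decisions use listings of accruing data, with no stated restriction to the PK population (SAP 3.1). A subject who discontinues may be replaced (Protocol 5.7). All of this stands and limits the severity. None of it gives a reason for the tracer condition.

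Note 1 on the Safety population is also not a direct precedent. It admits subjects given only CPHPC, who do not belong in a mAb PK set. It shows that All Treated was found too narrow for one purpose, and no more.

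A reader might infer that the rule selectively removes high-TMD subjects after infusion reactions. Protocol 3.4.1.2 does report reactions in most first-in-human subjects above 200 mg, but no passage links a reaction to omission of the tracer. Table 6 note 1 provides for pausing and resuming. The tracer may also start early in the infusion above 200 mg, and late at or below 200 mg after the first subject. Where the dose is escalated in session 2, a Part A subject with tracer in session 1 stays in the population.

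A reader might also see late tracer delivery as a route to mAb without tracer. Protocol 5.4 treats a tracer transport delay as a reason to delay mAb dosing itself, so it does not support that reading.

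**Conclusion.** The point holds as a defect of definition. Under the rule as written, a subject given unlabelled mAb and never the tracer loses all total-mAb PK displays, for a condition that this assay does not need and against the intention of Protocol 10.3.5. Its size is one subject in three within a part, or one in six overall, for each occurrence. How often it would occur is unknown. The conclusion rests only on the population definitions and on the tracer being a separate infusion. It does not rest on any claim about dose-dependent or tolerability-driven loss, which the documents do not establish. Severity: minor, an improvement at no cost.

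**What to change.** In SAP section 4, define the PK population as *all subjects who received any GSK2398852, labelled or unlabelled, and have at least one analysed PK sample*. Base the total-mAb displays on that set. Restrict the radio-PK displays to sessions in which the tracer was given.

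State how such a subject is grouped. PK is summarised by TMD, and TMD counts the 10 mg of tracer, so the planned label would be wrong. For example, a planned 500 mg becomes 490 mg if the unlabelled infusion is completed, and less if it is not. Show and group these subjects by the mAb mass actually received, with a footnote. The same applies to a Part A session without tracer in a subject who is retained because of the other session.

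Record the change in SAP 2.2 as a departure from Protocol 10.3.1. Protocol 10.3.5 already provides for documenting such changes in the analysis plan and the final report. The cost is one definition, one grouping rule and one line in SAP 2.2. No extra data are needed and the planned N does not change.
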